6. METHODS AND ASSESSMENTS

- a. Physical exam will be performed per usual care at TIRR, by the attending SCI physicians. Data will be retrieved from the electronic medical record and placed into the data spreadsheet. Missing data will be requested from the attending physician or directly from the patient.
- b. Transcutaneous Tibial Nerve Stimulation (TTNS) will be placed by trained research assistants in the clinic to determine if the subject meets I/E criteria. Skin inspection will be performed before and after the trial stimulation session at the electrode sites. Blood pressure will also be monitored during this trial for an additional safety measure to ensure autonomic dysreflexia is not occurring.
- c. The Bladder diary will be used to collect data use of TTNS with amperage and presence of toe flexion, pain score 0-10, as well as incontinence episodes and volumes. The research assistant (RA) will call weekly to capture the written data and monitor progress with the protocol.
- d. The RA will also perform the survey outcome measures (NBSS, I-QOL, CD-RISC, GSE, Medication adherence surveys and anticholinergic side effect questionnaire) at baseline every 4 weeks, 6 weeks and at 3-months. Surveys can be conducted over the telephone.

2. Randomization and Blinding

Subjects will be randomized to either TTNS or sham control (1:1) using a block size of 4 and stratified based on complete/incomplete SCI to ensure the equal allocation of the most severely injured in the two groups. The PI will be blinded to randomization and treatment allocation, managed by the research assistant.

3. Contraception and Pregnancy Testing

Females of childbearing age will have to adhere to medically recommended contraception if sexually active with men, such as condoms and/or birth control pills.

4. Study Visits and Procedures

- *Screening Visits and Procedures*

Screening will be performed in the SCI clinic by the PI or co-I SCI attendings.

Those that meet the I/E criteria will be approached for the study by the PI or co-I attendings. They have until the study period is complete to decide whether they want to participate. However, they will have to return to clinic to have the TTNS trial performed and the directions for home use.

- *Study Visits and Procedures*

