Subjects will have their first study visit after their normal clinic visit. Once consented, we will trial TTNS for a response of toe flexion. If they have a response, they will be included in the study. If no response or not tolerating electric stimulation, they will not be included in the study.

Participants will have direction in clinic on the use of the Stamobil+, including written, oral, and smartphone images/video if they have access.

The electric stimulation protocol will use stimulation frequency of 10 Hz and pulse width of 200ms in continuous mode for 30 minutes daily, beginning as soon as possible. The goal is 5 days per week of TTNS use for 3-months.

Subjects will be called weekly to capture the information of the TTNS log and to monitor progress of protocol. They will also be reminded to change electrodes weekly. 3 days prior to the NBSS call, the RA will contact the subjects to remind them to begin recording in their voiding diary for 2 days.

- *Final Study Visit:*

Upon completion of the 3-month study period, final voiding diary information will be collected and the post-trial questionnaires will be conducted.

- *Post Study Follow up and Procedures*

The data will be statistically analysed in the post-study follow up. Subject participation is not required.

- *Discontinuation Visit and Procedures*

If withdrawal occurs, no evaluation will be required for the final study visit, regardless of the withdrawal reason. There are no safety risks in withdrawing from this study at any point. OAB medications can be resumed at the prior efficacious dose.

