Patients will be randomized to control and TTNS at a 1:1 ratio by computer-generated sequences, with stratified allocation in blocks of 4 controlling for complete SCI, with the investigator blinded to the treatment allocation. Changes in outcomes listed in Aim 1 and 2 will be compared between groups by two-sample two-sided t-test or Wilcoxon rank-sum test. Descriptive statistics and mean plots will be provided for the longitudinal measurements. Multilevel mixed-effects regression models will be used for longitudinal analyses of treatment effects, controlling for confounding variables including age, sex, severity of SCI, compliance (number of sessions), and OAB medication dosages. Multiple testing will be adjusted by Bonferroni correction if necessary. Non-random missing data will be analyzed using the method in Ibrahim and Molenberghs.²³ Considering the unknown long-term effects of TTNS, we may not see significant treatment effect on some outcomes by conventional (frequentist) analyses. We plan a Bayesian analysis (with either skeptical or neutral priors) to estimate the probability (with 95% credible intervals) of treatment effect. Conventional analysis will be performed in SAS 9.4 (SAS Institute, Cary NC) and Bayesian analysis will be performed in R 3.5.0 using packages like R2WinBUGS.

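### The research assistant role both manages allocation and runs the entry test, with no concealment described and a fixed, stated block size of 4, so assignments may be foreseeable at entry

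*Combined protocol and SAP*

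**What the plan says.** The block size is given twice. Section 6 (Randomization and Blinding) sets a 1:1 allocation "using a block size of 4 and stratified based on complete/incomplete SCI". Section 11.2 repeats it: randomization is "by computer-generated sequences, with stratified allocation in blocks of 4 controlling for complete SCI".

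On who handles allocation, Section 6 says: "The PI will be blinded to randomization and treatment allocation, managed by the research assistant". No other member of staff is stated to be blinded, and the Blinding heading in Section 8 is marked not applicable.

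On who tests eligibility, Section 6, item b, says that the stimulation "will be placed by trained research assistants in the clinic to determine if the subject meets I/E criteria". Under Study Visits and Procedures the test follows consent and is decisive: "If no response or not tolerating electric stimulation, they will not be included in the study".

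Initial screening and the approach to patients belong to the PI or co-investigator attendings. The plan mentions no central or web system, no sealed envelopes and no list holder independent of the clinic staff. It does not say whether the arm is assigned before or after the stimulation test.

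**The concern.** Concealment means that whoever applies the last entry criterion cannot know the next arm. Here that criterion and the allocation sit with one role, and nothing in the plan keeps them apart.

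Knowledge of past arms is also easy to come by in that role. Under Section 6, item c, the research assistant telephones patients weekly and captures the diary, including amperage. Section 5 sets sham at 1 mA and reports about 40 mA for active stimulation in the pilot. With the block size known, past arms within a stratum point to the next one.

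If the next arm is foreseen, a borderline patient can be judged intolerant of stimulation, or a return visit can be brought forward or put off, with or without intent. Section 6 leaves room on timing, since patients have until the study period ends to decide and may come back for the test. Selection of this kind makes the arms differ at baseline in ways that randomization no longer balances and the analysis cannot reliably repair.

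**Working it through.** The plan states no figure for predictability, so there is none to reproduce.

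**Inputs.** Block size 4, ratio 1:1, two strata (Section 6, Randomization and Blinding; Section 11.2). Total enrolled 60 (Sections 3.1 and 11.1). The predictor is assumed to know the block size, the patient's stratum and all earlier assignments in the block.

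**Possible blocks.** Two of each arm in four places: 4!/(2! × 2!) = 6 equally likely sequences.

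**Known with certainty.** An assignment is certain once one arm has used both its places. **Best guess.** Name the arm that is behind, and toss a coin when level.

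| Place in block | P(known) | P(best guess right) |
|---|---|---|
| 1 | 0 | 1/2 |
| 2 | 0 | 2/3 |
| 3 | 2/6 = 1/3 (first two alike) | 1/3 × 1 + 2/3 × 1/2 = 2/3 |
| 4 | 1 | 1 |
| Sum | 4/3 | 17/6 |
| Divided by 4 | 33.3% | 70.8% |

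**Over 60 patients.** With complete blocks only: 15 × 4/3 = 20.0 certain, and 15 × 17/6 = 42.5 guessed correctly, against 30 by chance. If each stratum ends two patients into a block, there are 14 complete blocks: 14 × 4/3 = 18.7 certain (31%), and 14 × 17/6 + 2 × (1/2 + 2/3) = 42.0 guessed correctly. So the ranges are 18.7 to 20.0 certain and 42.0 to 42.5 correct.

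**If the predictor also holds the list.** All 60 are known and block size is irrelevant. The text does not exclude this.

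**Effect of changing the blocks.** The mixed design was simulated: 2,000 trials of 60 in one stratum, sizes 4 and 6 equally likely, with a predictor who knows those two sizes and every past assignment but not the size in use. The same simulation with fixed blocks of 4 gave 33.4% and 70.8%, matching the enumeration.

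| Design | Certain | Best guess right |
|---|---|---|
| Fixed 4 (as planned) | 33.3% | 70.8% |
| Fixed 6 | 25.0% | 68.3% |
| Random 4 or 6 | 5.7% | 69.1% |

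Varying the sizes removes most of the certainty but little of the guessing advantage. The resulting bias in the medication-reduction difference was not estimated: it would need the frequency of steering and the prognosis of those steered, and the documents give neither.

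**The case against.** Several points on the other side stand.

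- **Same role, not same person.** Item b speaks of research assistants in the plural; the randomization text speaks of one. A reader might infer that a single assistant tests and allocates. The documents do not establish that; they only leave it open.
- **The test is mostly objective.** Section 5 relies on visible toe flexion, so the discretion lies in tolerance and timing. Even tolerance is narrowed, because Section 5 has the intensity lowered if the patient perceives pain.
- **Entry is partly protected.** Section 3.1 calls for consecutive eligible clinic patients to be asked, attendings make the approach, and the PI is stated to be blinded. Section 5 expects 80 screened for 60 enrolled, so 80 − 60 = 20 losses are planned from all causes, and test failures are only part of these.
- **The block size is not the main defect.** With an exposed list it does not matter, and with varied sizes the guess rate barely moves. The leading gap is that concealment is unspecified.

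A reader might also infer that the PI can predict assignments, through diary amperages or the quarterly comparison with controls in Section 9.3. The PI does have access to study data, but the documents do not show the PI following individual amperages in order of entry, and a group comparison need not reveal the sequence. That is a separate question about blinding, and this point does not need it.

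These arguments narrow the opportunity. None of them supplies the missing separation of duties or order of events.

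**Conclusion.** The concern holds as a gap in allocation concealment, made worse by a fixed and stated block size. For anyone in the research assistant role who knows the earlier assignments, 33% of assignments are certain and 71% can be guessed, against 50% by chance. If that person also holds the list, the figure is 100%. These figures are conditional on that knowledge; they are not a measured property of this trial.

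It would go too far to conclude that enrolment will be or has been steered. The documents show an opportunity and no event, and they do not say when assignment occurs relative to the test. The planned sample size and power are unaffected. The change is worth making because it is cheap and because selection at entry is hard to undo later.

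**What to change.** **Main change.** Have the trial statistician, who is already involved under Section 9.3, generate and hold the list, out of reach of the PI and the research assistants. Release each assignment only after consent, the stimulation-test result, eligibility and stratum are irrevocably recorded. Where possible, the test should be done by a research assistant who does not know earlier assignments. This matters because late release alone does not stop a tester from predicting on the basis of past arms. State these arrangements in Section 6, and replace the not-applicable entry for Blinding in Section 8 with a cross-reference.

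**Secondary change.** Use randomly varied blocks within stratum (for example 4 and 6) and keep the sizes out of the protocol, in both Section 6 and Section 11.2. This supplements concealment and does not replace it.

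**Cost.** A new computer-generated list, a few sentences and some division of staff duties. The statistical downside is a slightly larger possible imbalance within a stratum at the end of accrual. If enrolment has begun, apply the change to the remaining assignments.

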- Potential for progressive SCI including neurodegenerative SCI, ALS, cancer myelopathy, Multiple sclerosis, transverse myelitis
- History of central nervous system disorder (i.e. prior SCI, stroke, brain injury, Parkinson's disease, MS, etc.)
- History of peripheral neuropathy
- pre-SCI symptoms of peripheral neuropathy (numbness and/or tingling in feet, sharp/jabbing/burning pain in feet, sensitivity to touch, lack of coordination, muscle weakness, etc.)
- Pregnancy
- Known injury to the lumbosacral spinal cord or plexus, or pelvis with associated neuropathy
- concern for tibial nerve pathway injury
- absence of toe flexion or autonomic dysreflexia during electric stimulation test
- bladder chemodenervation in prior 6 months

5. Withdrawal Criteria

Possible reasons for discontinuation of study intervention:

- Intolerable incontinence after discontinuation of bladder medications
- Intolerant to electric stimulation
- Non-compliance

To mitigate non-compliance, a stipend for effort in completing voiding diary will be provided at \$10 per day (2 days per month). An additional \$20 will be provided for logging bladder medication use and TTNS use/settings monthly. If both voiding diary and TTNS diary are reported, a \$10 bonus will be provided, therefore \$70 month 1, and \$50 for each months 2 and 3. At most per subject= \$170 for the 3-month trial per subject. Subjects will also receive reimbursement for travel for the urodynamic studies up to \$200 per trip (two urodynamic studies = up to \$400 per subject) and if medication reduction requires new prescriptions to cover co-payments when applicable up to \$50 total per subject.

6. Subject Replacement

Subjects who drop out will be replaced by recruitment from the SCI clinic and asking for informed consent from those who meet the I/E criteria.

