5. STUDY DESIGN

Anticipated number of patients to screen: 80

- Anticipated number of patients to enroll: 60
- Anticipated drop out or loss to follow-up: 6

Approximate time to complete study recruitment: 1 year

Expected duration of subject participation: 3-months. 3-months was selected as a fair assessment of efficacy. Clinically, medications are determined efficacious based on 1-month or less of use.

TTNS protocol: Same TTNS setting will be used as protocols HSC-MS-15-0806 and HSC-MS-17-0423. Electrodes 2 inch by 2 inch will be placed according to anatomic landmarks, with the negative electrode behind the internal malleolus and the positive electrode 10cm superior to the negative electrode, verified with rhythmic flexion of the toes secondary to stimulation of the flexor digitorum and hallucus brevis. The intensity level will be set to the amperage immediately under the threshold for motor contraction. If there is not contraction seen, patients will be excluded. In addition, if the patient perceives pain, the intensity will be lowered until comfortable. Stimulation frequency of 10 Hz and pulse width of 200ms in continuous mode will be used.^{13, 14}

Sham protocol and rationale: Toe flexion will be attempted, as in the TTNS protocol. Then the stimulation will be reduced to 1 mA for 30 minutes. Rationale: In order to make this a convincing blind, the TTNS protocol must be simulated closely as subjects may interact and discuss. Rather than turning the device off, they will be instructed that the stimulation required is below motor threshold, at 1 mA. Based on the knowledge of the pilot trial requiring about 40mA for TTNS, and the amperage for needle-driven PTNS adjacent to the tibial nerve at 0.5 – 1mA, it is unrealistic that 1mA via surface electrodes is sufficient to activate the tibial nerve. Both TTNS and sham participants will be instructed to use the device for 30 minutes, 5 days per week.

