Medication reduction protocol: Subjects will be using up to 2 anticholinergic OAB medications. Subjects generally use similar medications with a common approach- maximize one medication before adding a second medication. The PI will provide a weekly weaning schedule, individualized for each subject. No changes will occur during the first 2 weeks of TTNS. Starting week 3, the secondary OAB medication will be halved if possible, otherwise discontinued. Should the subject tolerate this, weaning will continue until one medication is discontinued, then the other. If the subject does not tolerate weaning, they will remain on the lowest, tolerable dose and we will attempt weaning the following week.

- Information gathered:
 - Clinical demographics, morbidity, and Neurologic Exam findings from interview with subjects, exam, and EMR review.
 - Bladder diary will include:
 - use of TTNS with amperage and presence of toe flexion, and pain score 0-10
 - log of catheterization, volumes
 - log of incontinence episodes
 - Description of other observed changes, including but not limited to: fatigue, vision changes, mental status, bowel program changes, and sexual function changes.
 - I-QOL at baseline initial visit and then at 3-month follow-up. Can be conducted over phone.

- NBSS at baseline and every 4 weeks (monthly) and at the 3-month follow-up. Can be conducted over phone.
- Anticholinergic survey at baseline and then at 3-month follow-up. Can be conducted over phone.
- TTNS satisfaction survey at 3-month follow-up. Can be conducted over the phone.
- Information will be tabulated on an Excel spreadsheet on my personal work desktop, password protected. Any paper data (bladder diary) will be de-identified and retained in a locked drawer in the locked office of the PI.
- General self-efficacy at baseline, week 6 and at the end of the trial. Can be conducted over the phone.
- CD-RISC at baseline, week 6 and at the end of the trial. Can be conducted over the phone.
- The medication and TTNS adherence survey at baseline then every 4 weeks. Can be conducted over the phone.
- The medication and TTNS % survey at baseline then every 4 weeks. Can be conducted over the phone.

1. Summary of Study Design

A randomized control trial of TTNS v sham-control in chronic SCI (n=60) performing intermittent catheterization on OAB medications will be performed to address the following Specific Aims:

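### The plan declares the PI blinded but does not keep the logged stimulation amperage, which effectively identifies the arm, from the PI, who individualises the weaning behind Primary Objective 1

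*Combined protocol and SAP*

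**What the plan says.** **The blind.** Section 6.2 (Randomization and Blinding) states "The PI will be blinded to randomization and treatment allocation, managed by the research assistant". Section 11.2 describes the randomisation "with the investigator blinded to the treatment allocation". Section 8.5, headed Blinding, is marked not applicable.

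**What is logged.** The bladder diary in section 5 (Information gathered) records "use of TTNS with amperage and presence of toe flexion, and pain score 0-10". Section 6, item c, describes the same diary as collecting stimulation use "with amperage and presence of toe flexion, pain score 0-10, as well as incontinence episodes and volumes". Section 3.5 pays subjects for "logging bladder medication use and TTNS use/settings monthly".

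**What the amperage shows.** In the sham arm toe flexion is attempted, and "Then the stimulation will be reduced to 1 mA for 30 minutes". The rationale for that level is "Based on the knowledge of the pilot trial requiring about 40mA for TTNS".

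**Who holds the records.** Section 5 has the gathered information tabulated on the desktop computer of the section's first-person author, and the de-identified paper diary locked in the PI's office. Section 10.2 puts voiding-diary and survey data in an online spreadsheet whose access the PI controls. Section 10.1 makes the PI solely responsible for accuracy and has the PI review anomalies. Section 14 has the PI retain all case report forms and source documents.

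**Who sets the weaning.** Section 5 (Medication reduction protocol) says "The PI will provide a weekly weaning schedule, individualized for each subject". Medication reduction is Primary Objective 1 (sections 2.2 and 2.4) and the basis of the sample size (section 11.1).

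**The concern.** A blind is only as good as the data flow behind it. Here the person declared blind has custody of, controls access to, or reviews records that appear to contain a field separating the arms by a factor of about 40. That person also makes a judgement that feeds directly into the primary outcome: how each subject's medication is stepped down. If the PI came to know a subject's arm, weaning might be pressed harder, or intolerance accepted more readily, in one arm than in the other. Part of the difference in medication reduction would then come from the weaning decisions and not from stimulation. No analysis could undo this afterwards, because the decisions would already have shaped the outcome.

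**Working it through.** The central check is a reading of the text.

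1. **Does the field identify the arm?** Sham is fixed at 1 mA. The active setting is just below motor threshold, lowered if painful, and the pilot needed about 40 mA. The ratio is 40 / 1 = 40. Active settings will vary, but one would have to fall close to 1 mA to be mistaken for sham. The entry is close to decisive.

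2. **Can it reach the PI?** Section 5 lists the bladder diary, including amperage, among the information gathered. It then has that information tabulated on the author's desktop and the paper diary kept in the PI's office. Section 10.1 adds an active duty, review of anomalies, and section 14 adds retention of all source documents. Retention alone shows custody, not reading.

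3. **Is it withheld anywhere?** Nothing in the available text masks amperage, restricts the PI's view of it, or delays that view until weaning ends or the database is locked.

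4. **Is there a separation that works indirectly?** Data are coded by subject ID and the RA holds the linking log (sections 10.2 and 12.3). This is a confidentiality measure, and it does reduce the risk. It does not clearly remove it: the PI obtains consent (12.1), sets weaning (5) and collects adverse events (9.2) in the same subjects, and the section 5 tabulation also holds demographics and examination findings.

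5. **Are settings in the same record as the bladder data?** The documents conflict. Sections 5 and 6 describe one bladder diary with amperage and incontinence together. Section 3.5 names a voiding diary and a TTNS diary, section 6.4 refers to a TTNS log apart from a two-day voiding diary, and section 10.2 names only the voiding diary and surveys as entered. On the second reading, amperage may not enter the PI-controlled spreadsheet. The case report form and sample diary, listed as appendices, might settle this but are not in the available text.

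6. **Does the PI have discretion?** The start week, the order of medications and the re-attempt the following week are common to both arms. Within that, the schedule is individualised, with no stated criterion for tolerance. Who judges tolerance is not stated.

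**Illustration only.** The plan gives no figure for this point. Its sample size supplies the setting. With 83% v 40%, mean 0.615, the pooled normal formula gives n = [1.96√(2 × 0.615 × 0.385) + 0.842√(0.83 × 0.17 + 0.40 × 0.60)]² / 0.43² = 18.9, so 19 per arm (24 with continuity correction). The stated 21 lies between, and this point does not alter it.

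Now suppose the true reduction rate is 40% in both arms and that knowledge of the arm opens an assumed gap, giving rates of 0.40 ± gap/2. Exact enumeration of two-sided 5% tests gives these chances of a significant result:

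| Per arm | Gap | Fisher | t-test on 0/1 data | Pooled z |
|---|---|---|---|---|
| 30 | 0 | 0.026 | 0.049 | 0.049 |
| 30 | 10 points | 0.076 | 0.122 | 0.122 |
| 30 | 20 points | 0.259 | 0.351 | 0.351 |
| 21 | 0 | 0.020 | 0.043 | 0.050 |
| 21 | 10 points | 0.049 | 0.090 | 0.100 |
| 21 | 20 points | 0.158 | 0.242 | 0.261 |

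A 10-point gap is 0.10 × 30 = 3 subjects. Several tests are shown because section 11.2 names none for proportions. The gaps are invented inputs. The table shows only what such gaps would do if they arose.

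**The case against.** The strongest reply is that custody is not knowledge. The paper diaries are de-identified and locked away, the electronic data are coded, and the RA alone holds the link. No section says that the PI reads amperage or uses the diary to decide weaning. If the TTNS log is a separate record, the separation may already exist in practice. Tolerance may in effect be the subject's own report, and subjects receive a sham designed to be convincing.

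Much of this stands. A reader might infer that the PI is, or will be, unblinded. The documents do not support that: they show access and the absence of a barrier, not use. A reader might also infer that weaning will favour TTNS. That is not shown either, since the sequence is common to both arms and who assesses tolerance is unstated.

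Section 9.3 invites another strong reading: the PI and the statistician compare morbidity in participants with controls, which looks like by-arm data in the PI's hands. But section 2.4 frames the expectation as participants against non-participants, and section 9.3 itself refers to the wider SCI population, so a by-arm comparison is plausible but not certain. Even if it is by arm, aggregate rates alone do not reveal a subject's allocation.

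What does not stand is the idea that coding settles the matter. It does not hide the amperage, and anomaly review is an assigned task that can bring the PI to the entries.

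**Conclusion.** The point holds as an unprotected blind. Two sections promise a blinded PI. Following the data flow in section 5 puts an arm-revealing field within that PI's reach, and nothing in the available text keeps it back. Confidence is high on that silence and on the need to reconcile the sections. There is no comparable confidence that unblinding or bias would occur.

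The size of any bias cannot be told from the documents. The error rates in the table rest wholly on assumed gaps and are not grounds for the severity; with Fisher's test at 21 per arm, even a 10-point gap leaves the rate at 4.9%. The case for acting is that the field is close to decisive, the outcome concerned is Primary Objective 1, and the repair is cheap beforehand and impossible once weaning decisions are made. It should be fixed.

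A reader might extend the point to the RA, who manages allocation and also appears to give the surveys. The plan promises no masked interviewer, so that breaks no commitment. It calls for disclosure only and is not part of this finding.

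**What to change.** **Main change (sections 3.5, 5, 6, 10 and 14).** Keep amperage, toe-flexion entries and the allocation list in a separate TTNS log held by the RA, on paper and electronically, and withheld from the PI until database lock. The PI reviews anomalies on a sheet without these fields, and the RA checks the settings field. Allow release of settings to the PI where safety requires it, and log each release. Reconcile these sections so that they agree on whether there is one diary or two, what enters the spreadsheet and who can open each file. The weaning rules are not touched.

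**Secondary change (section 9.3).** State whether the morbidity comparison is by randomised arm. If it is, the statistician prepares the by-arm tables for the advisory board already named there, and the PI sees pooled data.

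**Cost.** Protocol wording, a separable log, a split file and changed access rights, with no added visits or calls for subjects. The same entries, at most 60 × 12 × 5 = 3,600 sessions, are filed apart. If the comparison is by arm, quarterly tables number about (12 + 3) / 3 = 5 with one year's recruitment. At Table 3's 2 to 6 subjects a month the range is (10 + 3) / 3 ≈ 4 to (30 + 3) / 3 = 11.

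**Downsides.** A little more RA and statistician work, some board reading time if the comparison is by arm, and settings anomalies that the PI does not review before lock. The PI grades adverse events and would do so without the setting unless it is released. Pain scores remain visible to the PI and could still hint at the arm.

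### The research assistant role that manages allocation also administers the NBSS, I-QOL and side-effect surveys, and no blinded interviewer is specified

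*Combined protocol and SAP*

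**What the plan says.** Section 6.2 (Randomization and Blinding): "The PI will be blinded to randomization and treatment allocation, managed by the research assistant". Section 11.2 repeats the PI's blind: "with the investigator blinded to the treatment allocation". Section 8.5, headed Blinding, is marked not applicable.

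Section 6, item c: "The research assistant (RA) will call weekly to capture the written data and monitor progress with the protocol". The diary contents listed in section 5 include "use of TTNS with amperage and presence of toe flexion, and pain score 0-10".

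Section 6, item d: "The RA will also perform the survey outcome measures (NBSS, I-QOL, CD-RISC, GSE, Medication adherence surveys and anticholinergic side effect questionnaire". The same item adds "Surveys can be conducted over the telephone". The schedule of events in section 5.1 goes further. Its footnote marks the NBSS at weeks 4, 8 and 12, and the I-QOL and anticholinergic survey at week 12, as telephone assessments.

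Participants are blinded through the sham procedure in section 5: toe flexion is attempted in both arms, and the sham device then runs at 1 mA. No section names an interviewer or outcome assessor who is kept unaware of the arm.

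On staffing, section 6, item b says the trial stimulation "will be placed by trained research assistants in the clinic to determine if the subject meets I/E criteria", in the plural. Items c and d, section 6.2, and sections 10.2 and 12.3 speak of a single research assistant.

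**The concern.** The NBSS is a measure for Primary Objective 2, the I-QOL for Secondary Objective 1 and the anticholinergic survey for Secondary Objective 2. All three are subjective. Under the schedule, every post-baseline score on them comes from a spoken exchange with the role that manages allocation. Prompting, tone, or the way an unclear answer is resolved can then differ between arms without intent. The sham was designed with care to protect these comparisons, and this arrangement weakens that protection at the point of measurement. Such an influence would look like a treatment effect, and no analysis in section 11.2 could separate the two afterwards.

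**Working it through.** **1. Who does what.** This part is a comparison of sections; the plan gives no figure to reproduce.

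| Duty | Assigned to | Where |
|---|---|---|
| Managing randomization and allocation | research assistant | 6.2 |
| Weekly calls and stimulation log | research assistant | 6, item c; 6.4 |
| NBSS, I-QOL, CD-RISC, GSE, medication adherence and anticholinergic surveys | research assistant | 6, item d |
| TTNS satisfaction survey | no one named | 5 |
| Stated to be blinded | PI/investigator; participants by sham design | 6.2, 11.2; 5 |
| Blinded interviewer | none named | – |

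**2. Would moving the allocation list be enough?** No. The weekly log contains the amperage. Section 5 sets sham at 1 mA and reports about 40 mA for active stimulation in the pilot. Whoever takes the log can infer the arm without the list, so a blinded interviewer must have neither.

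**3. What could an interviewer shift do?** This is illustrative only; the documents give no size for such a shift.

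Inputs:
- Two-sample, two-sided t-test (section 11.2) at 0.05 (section 11.1), without the Bonferroni correction that 11.2 leaves open.
- NBSS SD of 11. Section 11.1 prints 11.8 (11) for change after chemodenervation without labelling the bracket; reading it as an SD is an assumption.
- 21 per arm (the calculated size) and 30 per arm (the number recruited, so no losses).
- True effect zero; assumed between-arm shift δ of 1, 2, 3 or 5 points.

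Formula: the test statistic follows a noncentral t distribution with 2n − 2 degrees of freedom (40 or 58) and noncentrality λ = (δ/11) × √(n/2). The false-positive rate is the probability that |t| exceeds the two-sided 5% critical value. √(21/2) = 3.240 and √(30/2) = 3.873.

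| δ | δ/11 | λ, 21 per arm | Rate | λ, 30 per arm | Rate |
|---|---|---|---|---|---|
| 1 | 0.091 | 0.29 | 6.0% | 0.35 | 6.4% |
| 2 | 0.182 | 0.59 | 8.9% | 0.70 | 10.7% |
| 3 | 0.273 | 0.88 | 13.9% | 1.06 | 18.0% |
| 5 | 0.455 | 1.47 | 30.1% | 1.76 | 41.0% |

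For the I-QOL, the same calculation with the pilot SD of 17 gives 7% to 15% (21 per arm) and 7% to 20% (30 per arm) for shifts of 2 to 5 points. Section 11.1 plans with an SD of 4, under which the same shifts would matter much more; 17 is the observed and milder choice.

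**The case against.** The strongest reply is that the respondent's blind is what chiefly protects a patient-reported score, and this trial has one. Participants are told that the required stimulation lies below motor threshold, and the sham device stays on. The PI, who issues the weaning schedule, is blinded too. What remains is the influence of an informed interviewer on a blinded respondent, which is a smaller risk than an unblinded participant. This stands, and it keeps the point at a moderate grade. It does not remove the point, because the interviewer's knowledge is avoidable.

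A second reply concerns feasibility. A reader might infer from the plural in section 6, item b that the duties can be divided at no cost. The documents do not support that. The plural refers to electrode placement at the eligibility test, other sections use the singular, and neither the number of assistants nor their availability is given. Self-completion has limits too: section 3.2 expects that people with tetraplegia will be unlikely to be able to sign, so an unknown share would need the forms read to them. Both limits stand and shape the fix.

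A third reply is that the 3- and 5-point shifts are arbitrary. They are assumptions, and at 1 point the inflation is slight. Losses also matter: section 5 expects 6 and section 11.1 allows 40%, so 30 per arm is an upper bound. The conclusion rests on the division of duties and does not need any particular shift.

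**Conclusion.** The point holds in a limited form. As written, the role that knows the arm collects the NBSS, the I-QOL and the anticholinergic survey by telephone after baseline, and the plan provides no blinded interviewer. One person doing all of this is the natural reading but is not stated outright. The size of any bias is unknown; under the assumptions above, the NBSS false-positive rate runs from about 6% to 41%, depending on the shift and the number analysed.

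Three stronger readings are tempting and not supported:
- That only the PI is blinded. Participants are blinded by the sham.
- That the research assistant gives every questionnaire. Item d lists six instruments, and no administrator is named for the satisfaction survey.
- That the medication-reduction endpoint, which drives the sample size, is compromised in the same way. The PI who sets the weaning schedule is stated to be blinded, and the documents do not show that this endpoint is affected.

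The change should be made before outcome data are collected.

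**What to change.** Amend section 6, item d, and the telephone footnote of the schedule of events. Suggested wording:

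*Participants complete the NBSS, I-QOL and anticholinergic side-effect survey themselves, online or on paper. Where hand function prevents this, the items are read verbatim from a script. The mode of administration is recorded for each assessment.*

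If more than one research assistant is already available, add to sections 6.2 and 6, item d:

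*The surveys, any reading aloud and the continence part of the voiding diary are handled by a research assistant who neither holds the allocation nor takes the amperage log.*

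The diary belongs in this sentence because it shares Primary Objective 2 with the NBSS and is now collected on the same call as the amperage.

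The cost is protocol wording and, where staffing allows, a division of duties; no new post is asked for. The downsides are possibly more incomplete forms, some mixing of modes and less flexible scheduling. If there is only one research assistant, participants who need reading aloud remain exposed to an informed interviewer, and the continence diary stays on the same call as the amperage log. Recording the mode allows a sensitivity analysis restricted to self-completed forms.
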